
MK-8521-004-02 Final Protocol

Confidential

21-Dec-2016

Protocol/Amendment No.: 004-02

Protocol/Amendment No.: 004-02

12.4 Mapping of Relative Day Ranges to Weeks

The following will be used to map the relative day ranges to weeks, as described in **Section 8.2**.

Mapping of Relative Day Ranges to Weeks

Required Phase	Relative Day Range	Week
	Day Relative to Start of Trial	
_	Visit <2 and Day <1	$min(Day/7^{\dagger}, -2)$
Placebo Run-in	Visit ≥2 and Visit <3 and Day <1	-2
Placebo Run-in	Visit ≥3 and Day ≤1	0
Treatment	$2 \le \text{Day} \le 52$	6
Treatment	$53 \le \text{Day} \le 73$	9
Treatment	74 ≤ Day	12
† Truncated to the largest integer less than or equal to this ratio.		

Protocol/Amendment No.: 004-02

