4.2.3 Rationale for Endpoints

4.2.3.1 Efficacy Endpoints

Efficacy endpoints will be assessed after 12 weeks of daily dosing and will include change in glycemic parameters and change in body weight.

Glycemic efficacy endpoints will include the changes from baseline in A1C and FPG at Week 12. A1C reflects average glucose concentrations over the past 3-4 months and, therefore, provides a useful index of the glycemic control of treatment with MK-8521 over that time period. It is a standard efficacy endpoint used to assess the glycemic efficacy of AHAs. A1C is a key glycemic parameter which correlates with reduction of risk of diabetic microvascular complications. The measurement of FPG will provide in sight into the effects of treatment with MK-8521 on this endpoint and characterize the earlier time course of glucose control in this trial.

Body weight reduction is an anticipated outcome of co-activation of GLP-1R and GCGR. Body weight loss may also drive A1C reduction at a modeled rate of 0.1% reduction in A1C for every 1 kg reduction in body weight. While the trajectory of reduction in A1C achieved with GLP-1R activation (as observed with liraglutide) reaches near maximal efficacy at 12 weeks, further potential weight loss past 12 weeks with MK-8521 may lead to further reduction in A1C. Data regarding body weight loss collected throughout the 12 week treatment period will be used to model further weight loss and subsequent A1C reduction up to 24 weeks.

Other efficacy endpoints that will be assessed include changes from baseline at Week 12 in fasting plasma lipid profile (including LDL-cholesterol, HDL-cholesterol and triglycerides), and blood pressure. These are clinically meaningful metabolic endpoints that may change

Protocol/Amendment No.: 004-02

with body weight loss. Moreover, glucagon receptor activation has previously been implicated in several studies as causing a reduction in LDL-cholesterol.

Efficacy endpoints obtained from both MK-8521 arms will be interpreted vs. placebo and vs. results collected in the liraglutide-treated arm.

There exist limitations of the comparisons to liraglutide, as liraglutide will be dispensed as an open label medication and MK-8521 as blinded. Data may be confounded by subjective assessments, compliance, or other affects based upon subject and investigator knowledge of the assigned therapy in the liraglutide arm. To mitigate these effects, previously published liraglutide data will be taken into account.

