4.2.3.2 Safety Endpoints

Safety assessment will include collection of adverse events (including reports of nausea, vomiting or injection site reactions), a hypoglycemia assessment log to collect information on each potential episode of hypoglycemia (including concurrent fingerstick glucose value) and physical examination including vital signs. Incidence of adverse events of symptomatic hypoglycemia is defined as a Tier 1 pre-specified safety parameter. Tier 1 pre-specified safety parameters are parameters subject to inferential testing.

Due to a potential increase in HR as detailed in section 4.1.2, HR will be monitored at all study visits. Discontinuation criteria that incorporate parameters of increase in HR [Tachycardia (HR >100 bpm) of any duration associated with symptoms, sustained resting HR >100 bpm and sustained increase from baseline in resting HR ≥30 bpm] have been outlined and provide boundaries of tolerance for increase in HR (see Section 5.9). Based on prior studies with liraglutide, it is anticipated that agonism of the GLP-1 receptor may result in a low rate of patients meeting the discontinuation criteria for an increase in heart rate. In the event of ≥5 subjects (potentially comprising over 10% of subjects in a single study arm) discontinuing blinded investigational product (MK-8521 or matching placebo) due to meeting the defined criteria for discontinuation due to an increase in HR, a review of unblinded safety data by a Standing Internal Data Monitoring Committee (siDMC) will be triggered. If a clear disparity is observed between the different study arms in the allocation of the discontinued subjects the siDMC may decide to continue or stop the study, or stop or modify the study arm. For further details on the siDMC, see the siDMC charter and Section 7.3.2.

Key endpoints for HR that will be assessed will include change from baseline at Week 12, events of sustained increase from baseline in resting HR \geq 30 bpm from baseline, events of sustained increase in resting HR > 100 bpm and tachycardia (HR >100 bpm) of any duration associated with symptoms.

Laboratory safety studies will include blood chemistry, lipid panel, hematology, urinalysis and electrocardiograms (ECGs). Refer to Section 6.0 and Section 7.1.3.1 for further details.

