Witness Dose of Blinded Investigational Product / Open-Label Liraglutide in Clinic ⁱ			X	X	X	X	X	X	X	X			

Protocol/Amendment No.: 004-02

Trial Period:	Scree	ning	Run- In	Random- ization				Treatment				Post-T	reatment
Visit Title	Screen- ing	Wash- out	Run- in	Random- ization	Week 1	Week 2	Week 3	Week 4	Week 6	Week 9	Week 12	Discontinu ation Visit	Follow-up Day 14
Visit Number	1	1A ^w	2	3	4	5	6	7	8	9	10	Discontin- uation	14-Day Post Treatment Follow-Up Visit ^b
Scheduled Week		-10	-2 (Day -14)	0 (Day 1)	1 (Day 7)	2 (Day 14)	3 (Day 21)	4 (Day 28)	6 (Day 42)	9 (Day 63)	12 (Day 85)	At time of discontinuation ^a	14 days after last dose
Suggested Visit Window				+/- 3 days	+/- 3 days	+/- 3 days		+/- 3 days					
Assess Trial Medication Compliance. Collect Unused and Used Investigational Product / Open Label Liraglutide ^g				X	Х	X	X	Х	X	Х	X	X	
Clinical Procedures/Asses	sments												
Demographics and Medical History	X												
Height	X		X										
Body Weight	X		X	X	X	X	X	X	X	X	X	X	X
Vital Signs (HR and Blood Pressure) ^j	X		X	X	X	X	X	X	X	X	X	X	X
Postural Blood Pressure/HR ^k			X										
Full Physical Examination (excluding rectal and urogenital examination)			X										
Brief Physical Examination ¹				X					X		X	X	
12-Lead ECG ^m			X	X							X	X	
Fasting Fingerstick Glucose in Clinic				X	_								
Review of SMBG Measurements and HAL				X	X	X	X	X	X	X	X	X	
Adverse Events Monitoring		X									X	X	X

Protocol/Amendment No.: 004-02

Trial Period:	Scree	ning	Run- In	Random- ization				Treatment				Post-T	reatment
Visit Title	Screen- ing	Wash- out	Run- in	Random- ization	Week 1	Week 2	Week 3	Week 4	Week 6	Week 9	Week 12	Discontinu ation Visit	Follow-up Day 14
Visit Number	1	1A ^w	2	3	4	5	6	7	8	9	10	Discontin- uation	14-Day Post Treatment Follow-Up Visit ^b
Scheduled Week		-10	-2 (Day -14)	0 (Day 1)	1 (Day 7)	2 (Day 14)	3 (Day 21)	4 (Day 28)	6 (Day 42)	9 (Day 63)	12 (Day 85)	At time of discontinuation ^a	14 days after last dose
Suggested Visit Window				+/- 3 days	+/- 3 days	+/- 3 days		+/- 3 days					
Laboratory Procedures/A	ssessmen	ts										-	
FPG	X		X	X	X	X	X	X	X	X	X	X	
A1C ^{n,x}	X		X ^x	X					X	X	X	X	
Fasting C-peptide ^o	X												
Lipid Panel ^p				X							X	X	
Chemistry Panel	X		X ^x	X				X		X	X	X	X
Hematology	X		X ^x	X				X			X	X	X
Fasting Triglycerides	X		Xz										
Serum Lipase	X			X				X			X	X	
Serum Calcitonin Level				X							X	X	
Fasting Insulin (potential analysis, for archive) and C-peptide ^q				X							X	X	

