8.2.3 Analysis Endpoints

Efficacy and safety endpoints that will be evaluated for within- and/or between-treatment differences are listed below.

The primary time point of the study is Week 12.

The baseline value will be defined as the **Visit 3/Day 1** (Randomization) measurement. If this measurement is not available, the following pre-randomization measurement will be used as the baseline value.

Regimen at Visit 1/Screening	Baseline value		
On metformin monotherapy (no washout)	If the Visit 3 measurement is missing, the Visit 1 measurement will be used. If neither measurement is available, the baseline value will be treated as missing		
On dual therapy metformin and a second AHA (enter washout)	If the Visit 3 measurement is missing, the Visit 2 measurement will be used. If neither measurement is available, the baseline value will be treated as missing		

The mapping of relative day ranges to Week is provided in Section 12.4.

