8.2.3.2 Safety Endpoints

Safety and tolerability will be assessed by a clinical review of all relevant adverse experiences and monitoring variables related to blood chemistry, hematology, vital signs, and ECG.

Tier 1 safety endpoints are adverse events of symptomatic hypoglycemia (see Table 13).

Tier 2 safety endpoints include changes from baseline in HR at different time points.

Adverse events (overall summary, specific AEs, and AEs by system organ class) and PDLCs in laboratory and vital signs parameters (including proportion of subjects with HR>100 bpm or HR increase > 30 bpm) will be classified as belonging to "Tier 2" or "Tier 3", based on the number of events observed.

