8.2.5.1 Efficacy Analyses

To address the primary objective, the analysis of change from baseline in A1C at Week 12 will be performed using a constrained longitudinal data analysis (cLDA) method proposed by Liang and Zeger. This repeated measures model assumes a common mean across treatment groups at baseline and a different mean for each treatment at each of the post-baseline time points. The response vector consists of baseline and the values observed at each postbaseline time point. The cLDA model will include terms for treatment, time, stratification factors of A1C (<8.5%, $\ge8.5\%$), BMI ($<30 \text{ kg/m}^2$, $\ge30 \text{ kg/m}^2$) and AHA washout status (Yes, No), and the interaction of time by treatment. Time is treated as a categorical variable so that no restriction is imposed on the trajectory of the mean over time. An unstructured covariance matrix will be used to model the correlation among repeated measurements and hence avoids the potential bias that could result from the use of specific structured covariance models. If the unstructured covariance model fails to converge with the default Newton-Raphson algorithm, the Fisher scoring algorithm or other appropriate methods can be used to provide initial values of the covariance parameters. In the rare event that none of the above methods yield convergence, a structured covariance such as Toeplitz can be used to model the correlation among repeated measurements. In this case, the empirical option will be used because the sandwich variance estimator is asymptotically unbiased while the model-based variance estimator can substantially overestimate or underestimate the true variance. The Kenward-Roger adjustment will be used with restricted (or residual) maximum likelihood (REML) to make proper statistical inference. The cLDA model uses the maximum likelihood principle to estimate the parameters and account for missing data in an implicit fashion.

The primary hypothesis will be assessed by an ordered testing procedure, comparing each of the two MK-8521 doses to placebo at Week 12, using the above cLDA model. This testing procedure first tests the 300 μg dose. If a statistically significant result (i.e., p<0.05) is observed on the 300 μg dose, the primary hypothesis (for A1C) is considered met and then the 180 μg dose is tested. The secondary hypotheses (for body weight and FPG) will be assessed only if the primary hypothesis is met, regardless of the outcome of the 180 μg vs placebo comparison.

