
Protocol/Amendment No.: 004-02

In the event that fewer than 75% of the subjects in the 300 μ g dose group receive the full target dose, suggestive of dose-intolerance, the hypothesis test MK-8521 180 μ g vs. placebo will be performed first. In this case if the 180 μ g dose vs. placebo is statistically significant, the primary hypothesis (for A1C) will be considered met and then the 300 μ g dose will be tested.

If success is achieved in the test of the primary hypothesis (i.e., at least one dose of MK-8521 provides significantly greater reduction in A1C relative to placebo following the testing procedure described above), then each of the MK-8521 doses will be compared to liraglutide using the same ordered testing procedure above. Continuous efficacy endpoints such as FPG, body weight, LDL-cholesterol level, HDL-cholesterol level, triglyceride level, systolic blood pressure (SBP), and diastolic blood pressure (DBP) will be analyzed using the above cLDA method described for A1C. Change and percent change from baseline in triglycerides will be analyzed using multiple imputation (MI) of missing values (if any) in conjunction with a robust regression (RREG) approach that uses M-estimation. Because the percent change in triglycerides typically has a skewed distribution, the cLDA model which is based on the symmetric normal distribution is not appropriate.

The primary (A1C) and key secondary endpoints (FPG and body weight) will also be analyzed in the PP population using an ANCOVA model. The ANCOVA model will include treatment, stratification factors of A1C (<8.5%, $\ge8.5\%$), BMI (<30 kg/m², ≥30 kg/m²) and AHA washout status (Yes, No), and baseline value. By definition, there will be no missing outcome data in the PP population.

Key efficacy endpoints will also be analyzed in the mFAS population using the same statistical methods stated for the FAS population.

Table 12 summarizes the analysis strategy for all efficacy endpoints. The strategy to address multiplicity issues with regard to multiple treatment comparisons and multiple endpoints is described in Section 8.2.6, Multiplicity.

Table 12 Analysis Strategy for Efficacy Endpoints

Endpoint (All at Week 12)	Approach	Statistical Method	Analysis Population	Missing Data Approach
Primary				
Change from baseline in A1C	P	cLDA	FAS	Model-based
Change from basefine in ATC	S	ANCOVA	PP	NA
	S	cLDA	mFAS	Model-based
Key Secondary				
Change from baseline in FPG	P	cLDA	FAS	Model-based
	S	ANCOVA	PP	NA

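### Section 12.4 labels every treatment value from Day 2 to Day 52 as Week 6, so five of the seven weight, FPG, BP and HR visits share one label with no rule for choosing among them (minor)

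*Combined protocol and SAP*

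**What the plan says.** - **The table (Section 12.4).** "The following will be used to map the relative day ranges to weeks". The three treatment-phase rows are contiguous: Day 2-52 is Week 6, Day 53-73 is Week 9, and Day 74 onward is Week 12.
- **Its scope (Section 8.2.3).** Under an introduction covering efficacy and safety endpoints alike, the plan says: "The mapping of relative day ranges to Week is provided in Section 12.4". It is not limited to A1C.
- **The schedule (Section 6.0).** After baseline, A1C is taken at Weeks 6, 9 and 12. Weight, FPG, BP and HR are taken at Days 7, 14, 21, 28, 42, 63 and 85. Section 4.2.3.2 adds that "HR will be monitored at all study visits".
- **The model (Section 8.2.5.1).** The cLDA has categorical time, unstructured covariance and "a different mean for each treatment at each of the post-baseline time points". Weight, FPG and BP use the same model as A1C.
- **Early outputs.** Section 8.2.3.2: "Tier 2 safety endpoints include changes from baseline in HR at different time points". Table 13 requires a 95% CI for treatment comparisons of HR change. Section 4.2.3.1 says that FPG will "characterize the earlier time course of glucose control in this trial" and that weight collected through the 12 weeks will be modelled.
- **Record selection.** Section 8.2.3 gives a fallback for a missing baseline. Sections 7.1.2.1 and 7.1.2.3 deal with replicates within one visit. No rule chooses between visits that share a label.

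**The concern.** The cut points suit A1C and none of the other main parameters. Applied as written, the table causes three problems.

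1. **Ambiguous input to the cLDA.** The model needs one value per subject per time point. For weight and FPG, the key secondary endpoints, up to five scheduled values qualify as Week 6. Two programmers could choose differently and both comply. Section 8.2.9.2 takes the interim conditional SD for weight from the same model, so the choice should be on paper before any unblinding.
2. **Early time points merged.** Weeks 1-4 have no label of their own for the Tier 2 HR change or for the early FPG and weight course. Visit-day doses follow all procedures (Section 5.2.2), and the 300 µg dose starts at Visit 6/Day 21 (Section 2.1). On schedule, the Day 7, 14 and 21 values in the 300 µg arm therefore precede the first 300 µg dose, yet carry the Week 6 label.
3. **Wrong label on safety laboratory values.** Chemistry, hematology and lipase are sampled at Week 4 and not at Week 6. A by-week summary built from the table would show the Week 4 values as Week 6.

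**Working it through.** **Step 1. Apply the table to the scheduled days, each also at ±3 days (Section 7.1.5.2).**

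| Parameter | Labelled Week 6 | Week 9 | Week 12 |
|---|---|---|---|
| A1C | Week 6 | Week 9 | Week 12 |
| Weight, FPG, BP, HR, PK trough | Weeks 1, 2, 3, 4, 6 | Week 9 | Week 12 |
| Chemistry | Week 4 | Week 9 | Week 12 |
| Hematology, lipase, anti-drug antibody | Week 4 | none | Week 12 |
| Glucagon receptor biomarkers | Weeks 1, 2, 4, 6 | none | Week 12 |

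The ±3 days change no label. Five of seven weight, FPG, BP and HR visits share Week 6, and three of those five precede the first 300 µg dose in that arm.

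**Step 2. Reproduce the plan's figures (Section 8.2.7).** Inputs: 40 per arm; attrition 0.08 at Week 6 and 0.16 at Week 12; correlation ρ = 0.76732; SD 2.7 kg and difference 2 kg for weight; SD 40 and difference 30 mg/dL for FPG.

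Effective n per arm = 40 / [(1 − ρ²)/0.84 + ρ²/a], where a is the proportion of subjects supplying the intermediate record.

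With a = 0.92: 40 / (0.4896 + 0.6400) = 35.4. The plan gives 35.

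Power = Φ(d / (SD·√(2/n)) − 1.96). At n = 35.4 this is 87.6% for weight and 88.4% for FPG. The plan gives about 87% and 88%.

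**Step 3. Effect of the mapping on Week 12.** Assumptions: every early dropout (8%, or 0.08 × 40 = 3.2 per arm) supplies some 'Week 6' record, so a = 1; dropout is unrelated to response; the weight effect grows linearly to 2 kg at Day 85; the placebo course is flat; conditional SDs are equal.

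*(a) Closest record used.* Completers supply Day 42 and early dropouts an earlier day. Shift = 0.767 × 0.08 × (effect at Day 42 − effect at the record's day), with effect = 2 × day/85.
- All dropouts supply Day 7: 0.767 × 0.08 × (0.988 − 0.165) = 0.051 kg, or 2.5% of 2 kg.
- All dropouts supply Day 28: 0.767 × 0.08 × (0.988 − 0.659) = 0.020 kg, or 1.0%.
- Effective n with a = 1: 40 / (0.4896 + 0.5888) = 37.1. Power at 1.949 kg is 87.5%, against 87.6% with a correct Week 6 window.

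*(b) First record used for everyone.* All records come from the same day, so there is no shift. Only the correlation of that record with Week 12 matters.

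| Correlation with Week 12 | Effective n | Weight power | FPG power |
|---|---|---|---|
| 0 | 33.6 | 85.9% | 86.7% |
| 0.767 | 37.1 | 89.1% | 89.8% |

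Effective n equals 35.4 at a correlation of 0.566. Below that, power is lost, by at most 87.6 − 85.9 = 1.7 points for weight and 88.4 − 86.7 = 1.7 points for FPG.

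**Step 4. Simulation (12,000 runs, Monte Carlo SE 0.006).** The mean difference was 2.00 kg with the correct window, 1.94 kg (closest record, Day 7), 1.98 kg (closest record, Day 28) and 2.00 kg (first record, correlation 0). Effective n was 35.7, 36.6, 36.9 and 33.4. The Day 7 case (1.94 kg, n = 36.6) gives power of about 86.7%, slightly below the formula's 87.5%. Both are within 1 point of 87.6%.

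**Step 5. Dependence on the linear course.** As an extreme bound, let the whole 2 kg appear between Day 7 and Day 42. The shift is then 0.767 × 0.08 × 2 = 0.12 kg, about a tenth of the 1.23 kg half-width. Power at 1.877 kg and n = 37.1 is 84.9%, or 2.7 points lower.

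**The case against.** The strongest reply is that little of consequence depends on this. Table 12 places every efficacy endpoint at Week 12. The A1C schedule puts one visit in each bin. The scheduled Week 12 values of weight, FPG, BP and HR stand alone in theirs. Section 4.2.3.2 names HR change at Week 12 among the key HR endpoints. All of this stands, and it is why the point is minor.

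A second reply is that the sponsor may intend nominal visits for everything except A1C. The flow chart names each visit by week, and nothing forbids summaries by nominal visit. That is plausible, but it is not written, and Section 8.2.3 reads the other way. If it is the intent, one sentence would settle most of the matter.

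A reader might infer that Weeks 1-4 cannot be reported at all. The documents do not go that far. The mapping gives those weeks no label, which conflicts with HR change at different time points, but it does not prohibit visit-based tables. The laboratory relabelling likewise matters only if a by-week summary is produced from the mapping, since Table 13 asks only for descriptive statistics there.

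**Conclusion.** The point holds as a minor one. The stated rule gives wrong labels for Weeks 1-4 and leaves the weight, FPG and BP models with several candidate records for one time point. What suffers is the early HR, FPG and weight course, any by-week laboratory summary, and the reproducibility of the weight and FPG cLDA.

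A reader might infer that the primary result or the trial's power is at risk. The documents do not support that. Week 12 A1C is not materially affected. Week 12 weight and FPG are touched only through the intermediate records of subjects with missing Week 12 data and through the estimated covariance. Under the Step 3 assumptions the weight shift is about 0.05 kg (0.06 kg in simulation), towards no effect, and the power loss is under 2 points. Some choices of record would slightly raise power. The linear course is the assumption that matters most, and even the extreme bound in Step 5 stays near a tenth of the CI half-width.

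**What to change.** 1. **Section 12.4.** Keep the current table for A1C. Add a second table for every parameter measured at any of Weeks 1-4 (weight, FPG, BP, HR, safety laboratory tests, PK troughs, biomarkers, anti-drug antibodies):

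| Week | Days | Target day |
|---|---|---|
| 1 | 2-10 | 7 |
| 2 | 11-17 | 14 |
| 3 | 18-24 | 21 |
| 4 | 25-35 | 28 |
| 6 | 36-52 | 42 |
| 9 | 53-73 | 63 |
| 12 | 74 onward, treatment phase | 85 |

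The cuts follow the midpoints between target days (10.5, 17.5, 24.5, 35, 52.5, 74). They keep the existing 52/53 and 73/74 boundaries and give each visit, with its ±3 days, its own window.

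2. **Section 8.2.3.** When several records fall in one window, use the one closest to the target day, and the later one if tied. Apply this to A1C too. Assign on-treatment Discontinuation Visit values by study day. Exclude the 14-day post-treatment visit from Week 12.

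3. **HR.** Report HR change at Weeks 1-4 with the between-group 95% CIs that Table 13 requires.

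4. **Section 8.2.5.1.** State which time points enter the weight, FPG and BP cLDA. Using Weeks 6, 9 and 12, as for A1C, keeps 4 × 5/2 = 10 covariance parameters. Subjects who leave before Day 36 then contribute only baseline (effective n about 35.4, in line with the plan's 35). Using all scheduled weeks follows the present text literally and keeps those subjects' early values, but needs 8 × 9/2 = 36 parameters. Either is workable if stated before unblinding.

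The cost is one table, a few sentences and slightly more programming, with no burden on sites.
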